3.6 Risks and benefits

3.6.1 Potential benefit

Based on the established role of both B cells and T cells in the pathogenesis of Graves' disease, CFZ533 has a potential to become a novel therapy to address the underlying pathogenesis. CFZ533 has never been used in patients with Graves' disease. Therefore, no statement can be made of its efficacy for patients participating in this study at this stage.

3.6.2 Potential risks associated with CFZ533 administration and their mitigation

Currently, limited data exists regarding the use of agents that block the CD40/CD154 pathway. Preclinical and Phase 1 data for CFZ533 as well as data from compounds acting on the same pathway (i.e., CD40-CD154) have been taken into account to estimate the potential risks associated with CFZ533. The risks to patients in this trial will be minimized by adherence to the eligibility criteria, close clinical monitoring, avoidance of prohibited treatments and overall adherence to terms outlined in this protocol. The current IB (Section 6, Investigator Guidance) also provides detailed instructions regarding the risks and their mitigation.

Acute hypersensitivity

Hypersensitivity or infusion reactions can manifest with itching, flushing, headache, nausea/vomiting, hypotension, urticaria, bronchospasm, or angioedema.

In this study, CFZ533 will be administered as an intravenous infusion where such hypersensitivity reactions can still occur. Patients will be monitored for at least 2 hours after the completion of CFZ533 IV infusion at each visit.

Immunogenicity

Corporate Confidential Information

Extrapolation of immunogenicity risks from healthy subjects to Graves' disease patients is unknown and blood samples will be collected during this trial to assess the immunogenicity.

Infections

Subjects treated with CFZ533 may be at an increased risk of infection. CD40 ligation is linked to the functional activity of antigen presentation, as well as T-cell priming, B-cell differentiation, antibody production and immune memory.

Administration of CFZ533 is expected to result in general immunosuppression with a decreased capacity to mount a response to novel immunogens, including those of bacterial, viral, fungal and parasitic origin when full receptor occupancy has been achieved.

Although the ability to mount a primary immune response will be affected by CFZ533, the memory B-cell repertoire and immune recall response should remain intact and protective. In addition, subjects will have adequate preformed antibody to maintain protective humoral response for extended periods of time (months).

Corporate Confidential Information

In patients receiving weekly to bi-monthly administration of the parent antibody lucatumumab, the rate of infection was very low and similar to control, supporting these stated hypotheses. Patients with current, active or latent infection susceptible to reactivation will be excluded from entry into the present clinical study.

The risk of infection may increase if CFZ533 is combined with steroids or strong immunosuppressive drugs. Patients who are HIV-positive or have taken immunomodulatory drugs, such as cyclosporine A, methotrexate, and/or cyclophosphamide within 3 months at the baseline will be excluded.

Patients enrolled in the current study will be monitored regularly and carefully for signs and symptoms which might indicate a severe infection. Patients will be informed to contact the study physician if they present with signs and symptoms of an infection such as fever, nausea, myalgia, headache, arthralgia, chills, diarrhea, stiff neck, and malaise for further assessment and treatment if necessary.

Lymphadenopathy

Corporate Confidential Information

The investigator should pay special attention to lymph nodes in patients during physical assessments including unusual lymphadenopathy in the absence of infection.

Lymphoproliferative disorders

Corporate Confidential Information

The clinician should monitor hematology regularly for changes consistent with a lymphoproliferative disorder.

Pregnancy

Women of child bearing potential should be informed that taking the study drug may involve unknown risks to the fetus if pregnancy were to occur during the study and agree that in order to participate in the study they must adhere to the contraception requirement for the duration of the study. If there is any question that the subject will not reliably comply, they should not be entered in the study.

Thrombosis

It has been shown that monoclonal antibodies that bind to CD154 (CD40L), the natural ligand to CD40, are associated with a risk of thrombosis in both clinical studies and non-clinical studies in primates. Accordingly, the potential risk of thromboembolic events with CFZ533 has been thoroughly investigated during the process of development.

Corporate Confidential Information

Although the risk is hypothetical, hematologic and coagulation parameters will be regularly monitored in the current study.

Systemic inflammation and potential kidney injury

Corporate Confidential Information

Although not expected in this clinical study, the investigator will monitor for signs, symptoms and laboratory results consistent with clinically significant inflammation as well as for changes in renal function and signs of acute kidney injury as per local practice.

Vaccination

Vaccination of patients during treatment with CFZ533 and prior to clearance of the antibody is likely to result in therapeutic failure (i.e., non-protective antibody titers) due to the pharmacologic activity of CFZ533. For patients participating in this study, all vaccinations should be up to date based on local guidelines. Administration of live attenuated agents will be prohibited in patients receiving CFZ533 treatment in this study.

There may be other unknown risks to CFZ533 which may be serious and unforeseen.

Blood samples will be collected frequently during the study either via venipuncture or cannula. Approximately 460 mL of blood is planned to be collected over the study duration (~36-week) from each patient. Additional samples for monitoring of any safety findings would be in addition to this. This is not considered to be a risk for this population.

4 Population

The study population will be comprised of male and female patients 18 to 65 years of age with Graves' disease hyperthyroidism.

To ensure 12 completers, a total of approximately 15 patients will be enrolled to participate in this study.

The investigator must ensure that all patients being considered for the study meet the following eligibility criteria. No additional criteria should be applied by the investigator, in order to ensure that the study population will be representative of all eligible patients.

Patient selection is to be established by checking through all inclusion/exclusion criteria at screening and/or baseline. A relevant record (e.g. checklist) of the eligibility criteria must be stored with the source documentation at the study site.

Deviation from **any** entry criterion excludes a patient from enrollment into the study.

Replacement patients will be enrolled to replace patients who discontinue the study for reasons other than safety before having completed 4 weeks of treatment and 4 week efficacy and safety evaluations.

4.1 Inclusion criteria

Patients eligible for inclusion in this study have to fulfill **all** of the following criteria at screening:

1. Written informed consent must be obtained before any assessment is performed.
2. Male and female patients 18 to 65 years of age included.
 - Women of child-bearing potential must be willing to use the highly effective methods of contraception (definition in Exclusion criteria #24) during the study treatment epoch and for 12 weeks after the last study treatment.

3. Graves' hyperthyroidism ([Baskin et al 2002](#)) with the following labs measured at screening:
 - TSH<LLN and either FT3>ULN or FT4> ULN
4. Patients must weigh at least 40 kg to participate in the study
5. Able to communicate well with the investigator, to understand and comply with the requirements of the study.
6. Patients have received up to date required vaccinations based on local guidelines.

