2.2 Secondary objective

Objective	Endpoint

To assess the safety and tolerability of CFZ533 (10 mg/kg IV for 12 weeks) up to 36 weeks	
Adverse events

[figure not shown]
Corporate Confidential Information

3 **Investigational plan**

3.1 **Study design**

This is a non-confirmatory, open-label, one treatment arm study in patients with GD.

A total of approximately 15 patients will be enrolled and treated with CFZ533 to ensure approximately 12 completers. For each patient, the study will consist of a screening epoch of up to 28 days, a baseline evaluation, a 12-week treatment epoch, 24-week follow up epoch after the last dosing of CFZ533 on Study Day 85, and a study completion evaluation on Study Day 253. Patients who discontinue the drug before having completed 4 weeks of treatment and 4 week efficacy and safety evaluations will be replaced with a newly enrolled patient. The study completion assessments (End of Study; EOS) should be completed in patients who discontinue the study. The study design is presented in [Figure 3-1](#).

Figure 3-1 Study design

Patients who meet the eligibility criteria at screening will be admitted to baseline evaluations. Baseline evaluations may be started from Day -7 to allow completion of assessments prior to the treatment on Study Day 1. All baseline safety evaluation results must be available prior to dosing and meeting the eligibility criteria. The baseline visit (Visit 99) can be skipped and the baseline assessments would be completed prior to the study treatment on Day 1 (Visit 101) if Day 1 is scheduled within 7 days of the screening visit (Visit 1).

Eligible patients will enter the study to receive treatment with CFZ533 at 10 mg/kg IV over approximately one hour on Study Day 1. Patients will be monitored closely for at least 2 hours, at the discretion of the Investigator, after the completion of IV administration of CFZ533 for vital signs and adverse events, including development of an injection reaction.

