No comparator: No previous clinical experience with an anti-CD40 blocking agent in patients with GD exists. Given the nature of TSH as described above, the likelihood of observing a response to placebo is very low. Data provided in ([Heemstra et al 2008](#)) regarding the natural variability of TSH levels in this patient population in the absence of treatment were used to predict, via simulations, the proportion of patients treated with placebo that would be expected to rise above 0.3 mU/L within 12 weeks simply due to random variability. This proportion is predicted to be less than 1%. Corporate Confidential Information

Therefore, inclusion of a placebo arm is considered unnecessary.

Patient population: Graves' hyperthyroid patients Corporate Confidential Information

Withholding standard of care treatment: Withholding standard of care treatment for Graves' hyperthyroidism (ATD, radio-Iodine or surgery) for 12 weeks during the clinical study treatment period is justified for two reasons:

- 1) The presence of hyperthyroidism for 12 weeks is unlikely to result in permanent complications, especially when patients are adequately treated with beta blockers (e.g., if the heart rate is controlled)
- 2) A delay of 12 weeks is unlikely to impact the ultimate efficacy and safety of definitive treatment for Graves' hyperthyroidism. Patients will undergo rescue therapy with the standard of care for Graves' hyperthyroidism if they meet the stopping criteria.

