4.2 Exclusion criteria

Patients fulfilling **any** of the following criteria are NOT eligible for inclusion in this study. No additional exclusions may be applied by the investigator, in order to ensure that the study population will be representative of all eligible patients.

1. Use of other investigational drugs within 5 half-lives prior to first treatment.
2. History of hypersensitivity to vaccines, the study drug or to drugs of similar chemical classes (e.g. IgG₁-related biologic agents).
3. History of treatment of Graves' disease with radio-iodine ablation or thyroidectomy.
4. Current treatment with anti-thyroid drugs (methimazole or propylthiouracil) within one week of starting treatment. Discontinuation of ATD must not have been for the sole purpose of qualifying for this study; rather it should have been based on clinical considerations (e.g. lack of efficacy or safety/tolerability issues with ATD).
5. History of hyperthyroidism not caused by Graves' disease (e.g. toxic multinodular goiter, autonomous thyroid nodule, or acute inflammatory thyroiditis).
6. History or presence of thyroid storm (fever, profuse sweating, vomiting, diarrhea, delirium, severe weakness, seizures, markedly irregular heartbeat, yellow skin and eyes (jaundice), severe low blood pressure, and coma).
7. Previous treatment with a B cell-depleting biologic agent or any other immunomodulatory biologic agent (experimental or approved) within 5 half-lives prior to first treatment.
8. History of malignancy of any organ system (other than localized basal cell carcinoma of the skin), treated or untreated, within the past 5 years, regardless of whether there is evidence of local recurrence or metastases.
9. Significant illness which has not resolved within two weeks prior to initial dosing.
10. History of recurrent clinically significant infection or of recurrent bacterial infections with encapsulated organisms, including current, active or latent infection susceptible to reactivation.
11. History of primary or secondary immunodeficiency, including a positive HIV (ELISA and Western blot) test result at screening.
12. A positive Hepatitis B surface antigen or Hepatitis C test result at screening.
13. History or evidence of tuberculosis by either of the following tests at screening:
 - Positive PPD skin test (size of induration measured after 48-72 hours, and a positive result is defined as an induration of $\geq 5\text{mm}$ or according to local practice/guidelines) **OR**

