Study completion information																	X
TSH	X	X	X		X		X		X		X		X	X	X	X	X
Total and free T3 & T4	X	X	X		X		X		X		X		X	X	X	X	X
PK (CFZ533) ⁹			X	X	X	X	X	X	X	X	X	X	X	X	X		X
Free & total CD40 on B cells ⁵				X			X		X		X		X	X	X		X
Soluble CD40 ⁵				X			X		X		X		X	X	X		X
Soluble CD154 ⁵				X			X		X		X		X	X	X		X
Exploratory Biomarkers in Serum ⁶		X	X		X		X		X		X		X	X	X	X	X
Corporate Confidential	X	X	X		X		X		X		X		X	X	X	X	X
Corporate Co	X	X	X		X		X		X		X		X	X	X	X	X
Corporate Confidential Information			X ⁸														
Corporate Confidential Information		X ¹³									X						

¹ Visit structure given for internal programming purpose only

² Only those inclusion/exclusion criteria that are specific for baseline visit

³ Immunogenicity: 0-hour sample is taken **pre-dose**

⁴ Corporate Confidential Information

⁵ On days when patient is dosed, sample is taken **pre-dose** (0-hour)

⁶ Corporate Confidential Information

⁷ Corporate Confidential

Information

Corporate Confidential Information

⁹ 0-hour sample (or assessment) is taken **pre-dose**, 1-hour sample is taken 1 hour **AFTER** the END of infusion

¹⁰PPD or QuantiFERON TB-gold test

Corporate Confidential Information

¹²The baseline visit assessments can be completed on Day 1 (pre-dose) when the first dose (Day 1) is received within 7 days of the screening visit.

¹³These assessments will be completed prior to the study treatment on Day 1 (Visit 101, **pre-dose**) if Day 1 is scheduled within 7 days of the screening visit (Visit 1).

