11.4.1 Variable(s)

The effects of CFZ533 on thyroid function will be primarily assessed by the proportion of patients whose TSH levels normalize (above 0.35 mU/L) after 12 weeks of treatment. They will also be assessed by the difference in mean total T3 and free T4 between baseline and after 12 weeks of treatment.

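### A patient whose TSH is already above 0.35 mU/L before the first dose can count as a TSH responder

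*Protocol*

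**What the plan says.** **Entry.** Protocol 4.1 applies all inclusion criteria at screening, and inclusion 3 repeats this: Graves' hyperthyroidism "with the following labs measured at screening", namely "TSH<LLN and either FT3>ULN or FT4> ULN". Protocol 3.1 allows "a screening epoch of up to 28 days". The opening of Protocol section 4 speaks of "checking through all inclusion/exclusion criteria at screening and/or baseline", but footnote 2 of Table 8-1 limits the baseline check: "Only those inclusion/exclusion criteria that are specific for baseline visit". Protocol 3.1 requires only the baseline safety results to be back before dosing, and the synopsis lists TSH under efficacy/PD.

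**Anti-thyroid drugs.** Exclusion 4 (Protocol 4.2) bars "Current treatment with anti-thyroid drugs (methimazole or propylthiouracil) within one week of starting treatment". It adds that the drug must have been stopped for clinical reasons, with lack of efficacy or poor tolerability as examples. Investigators may not add exclusions of their own.

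**Response.** Protocol 11.4.1 defines the endpoint as the "proportion of patients whose TSH levels normalize (above 0.35 mU/L) after 12 weeks of treatment". SAP 6.1.1 says the same. Protocol 11.4.2 and SAP 6.1.3 test this proportion against 5% with a one-sided exact test at 10%, met by at least 3 of 12. Under Protocol 11.4.3, a patient who leaves early still counts if the last TSH, taken after 8 weeks, was above 0.35.

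**Samples.** Table 8-1 schedules TSH at screening, at baseline and pre-dose on Day 1.

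**The concern.** TSH is measured immediately before the first dose, but no visible rule uses that value for eligibility or for response. The word normalize suggests an abnormal starting value, yet the screening result alone would satisfy it.

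The most plausible route is recent anti-thyroid treatment. A patient screened 8 to 28 days before Day 1 may be taking such a drug at screening, stop at least a week before dosing for intolerance, and reach Day 1 with a TSH that rose under that drug. If TSH is still above 0.35 at week 12, the patient is a responder to CFZ533.

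There is no comparator to expose this. Protocol 3.2 does without placebo partly because fewer than 1% of patients are predicted to rise above 0.3 mU/L within 12 weeks by random variation. That prediction concerns patients without treatment. It does not cover a patient recently on an anti-thyroid drug, or one who starts above the cut-off. Because three responders are enough, one misattributed patient supplies a third of the evidence required.

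**Working it through.** **Inputs from the documents.** n = 12, at least 3 responders, null rate 5%, alternative 38%, one-sided 10% (Protocol 11.4.2 and 11.6). X is binomial throughout.

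**1. The plan's own figures.**
- Power: P(X ≥ 3 | 12, 0.38) = 1 − 0.0032 − 0.0237 − 0.0800 = 0.893. The plan states around 89%, so it reproduces.
- False-positive rate: P(X ≥ 3 | 12, 0.05) = 1 − 0.95^12 − 12(0.05)(0.95^11) − 66(0.05²)(0.95^10) = 1 − 0.5404 − 0.3413 − 0.0988 = 0.0196.

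The rule therefore runs at 2.0%, well inside its nominal 10%.

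**2. Upper bound.** Assumption, not in the documents: m of the 12 are above 0.35 on Day 1 and certainly stay there; the rest respond at the null rate. The rule then needs 3 − m responders among 12 − m.
- m = 1: P(X ≥ 2 | 11, 0.05) = 1 − 0.95^11 − 11(0.05)(0.95^10) = 1 − 0.5688 − 0.3293 = 0.102.
- m = 2: P(X ≥ 1 | 10, 0.05) = 1 − 0.95^10 = 0.401.

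**3. Staying above 0.35 is not certain.** Let s be the probability that one such patient is still above 0.35 at week 12, and count the patient as a non-responder otherwise. With P(X ≥ 3 | 11, 0.05) = 0.0152, the rate is (1 − s)(0.0152) + s(0.1019).
- s = 0.5: 0.0076 + 0.0509 = 0.059.
- s = 0.75: 0.0038 + 0.0764 = 0.080.
- The rate reaches 0.10 at s = (0.10 − 0.0152)/(0.1019 − 0.0152) = 0.98.

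For two such patients, s = 0.5 to 0.75 gives 0.146 to 0.259.

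**4. Lower background rate.** If the others respond at 1% rather than 5%, and s = 1, the rate is 0.005 for m = 1 and 0.096 for m = 2.

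**5. With the fix.** One patient already above 0.35 stays in the 12 as a non-responder, so at least 3 are needed from 11.
- False-positive rate: P(X ≥ 3 | 11, 0.05) = 0.015.
- Power: P(X ≥ 3 | 11, 0.38) = 0.852, down from 0.893.

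**The case against.** **The route is narrow.** The patient must be biochemically hyperthyroid at screening, including a raised FT3 or FT4, have TSH above 0.35 by Day 1, and still be above it 12 weeks later without anti-thyroid drugs. Those drugs are prohibited on study (Protocol 5.2), and SAP section 4 removes data after rescue from the inferential analyses. Protocol 1.1 cites 50–60% relapse after withdrawal, which argues against assuming that such a patient stays normal. SAP 1.4 also describes newly diagnosed disease, although no visible eligibility criterion requires it, and part of the population rationale in Protocol 3.2 is redacted. All of this stands. It makes the case uncommon but does not close it.

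**The planned outputs would show it.** SAP 6.1.2 summarizes responders at each timepoint and SAP 6.1.3.3 plots individual TSH profiles. In a non-confirmatory study of 12 patients, a high Day 1 value would be noticed. That is true, but the formal count against 3/12 would still include the patient, and any exclusion would then be decided after the data were seen.

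**Two stronger readings are tempting, and the documents support neither.**
- The entry and response cut-offs appear to coincide, since Protocol 11.4.3 calls 0.35 the lower limit of normal. A reader might infer that patients just below it will often cross by chance. The documents give neither a within-patient TSH variability nor a distribution of screening TSH, so no rate can be attached. The fix proposed here would also do little for such a patient.
- A reader might infer that the 5% null rate rests on the under-1% prediction. Protocol 3.2 uses that prediction to justify having no placebo arm; Protocol 11.4.2 and 11.6 give no derivation of 5%.

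**Conclusion.** The gap is real and should be closed: as written, TSH above 0.35 mU/L before the first dose does not prevent a patient from being counted as a TSH responder. The frequency cannot be determined from the documents.

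The 10.2% and 40.1% are upper bounds. They assume that one or two such patients are among the 12 and stay above 0.35 with certainty. They do not show that the trial exceeds its 10% error rate. With one such patient, the rate passes 10% only if the chance of staying above is about 98% or more. With two, it already exceeds 10% at a chance of 0.5, given the 5% background rate.

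The point therefore rests on the missing condition in the definition, and on how few responders decide the result, more than on any expected inflation.

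**What to change.** In Protocol 11.4.1 and SAP 6.1.1, define a TSH responder as a patient with Day 1 pre-dose TSH at or below 0.35 mU/L and week-12 TSH above 0.35 mU/L. A patient already above 0.35 on Day 1 stays in the denominator as a non-responder. Apply the same Day 1 condition to the carry-forward exception in Protocol 11.4.3 and SAP 6.1.3.1.

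This takes a sentence in each place and no new sample. The cost is power: one such patient among the 12 lowers it from 89.3% to about 85.2%.

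Optionally, also apply the TSH part of inclusion 3 to the latest result available before dosing. This needs more than a wording change. Baseline is nominally Day −1, samples are processed centrally (Protocol 10.2), and only safety results must now be back before dosing, so it is feasible only where laboratory turnaround allows. It may also add an occasional screen failure. The responder definition closes the gap in the analysis without it.
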